10.3 Recording of adverse events and serious adverse events

Adverse events will be recorded in WISER using a recognized medical term or diagnosis that accurately reflects the event. Adverse events will be assessed by the investigator for severity, relationship to the investigational product, possible etiologies, and whether the event meets criteria of an SAE and therefore requires immediate notification to AstraZeneca/MedImmune Patient Safety.

The following variables will be collected for each AE:

AE (verbatim)

The date and time when the AE started and stopped

The maximum CTCAE grade reported

Changes in NCI CTCAE grade

Whether the AE is serious or not

Investigator causality rating against durvalumab (yes or no)

Action taken with regard to durvalumab.

Administration of treatment for the AE

Weather the AE caused the patient's withdrawal from the study

Outcome

In addition, the following variables will be collected for SAEs as applicable:

Date AE met criteria for serious AE

Date Investigator became aware of serious AE

Seriousness of AE assessed per criteria in 10.1.2

Date of hospitalization

Date of discharge

Probable cause of death

Date of death

Autopsy performed

Description of AE

Causality assessment in relation to Study procedure(s)

Causality assessment in relation to Additional Study Drug

The grading scales found in the revised NCI CTCAE version 4.03 will be utilized for all events with an assigned CTCAE grading. For those events without assigned CTCAE grades, the recommendation in the CTCAE criteria that converts mild, moderate, and severe events into CTCAE grades should be used. A copy of the CTCAE version 4.03 can be downloaded from the Cancer Therapy Evaluation Program website (http://ctep.cancer.gov).

Events, which are unequivocally due to disease progression, should not be reported as an AE during the study.

10.3.1 Study recording period and follow-up for adverse events and serious adverse events

Adverse events and serious adverse events will be recorded from time of signature of informed consent, throughout the treatment period and including the follow-up period (90 days after the last dose of durvalumab. This applies also in the situation when Durvaluamb was discontinued and patient was removed from the clinical study.

During the course of the study all AEs and SAEs should be proactively followed up for each subject. Every effort should be made to obtain a resolution for all events, even if the events continue after discontinuation/study completion.

The investigator is responsible for following all SAEs until resolution, until the subject returns to baseline status, or until the condition has stabilized with the expectation that it will remain chronic, even if this extends beyond study participation.

Follow-up of unresolved adverse events

Any AEs that are unresolved at the subject's last visit in the study are followed up by the investigator for as long as medically indicated. After 90 days, only subjects with ongoing investigational product-related SAEs will continue to be followed for safety. AEs are documented in Appendix 7.

AstraZeneca/MedImmune retains the right to request additional information for any subject with ongoing AE(s)/SAE(s) at the end of the study, if judged necessary.

Post study events

After the subject has been permanently withdrawn from the study, there is no obligation for the investigator to actively report information on new AE or SAEs occurring in former study subjects after the 90-day safety follow-up period for patients treated with durvalumab. However, if an investigator learns of any SAEs, including death, at any time after the subject has been permanently withdrawn from study, and he/she considers there is a reasonable possibility that the event is related to study treatment, the investigator should notify AstraZeneca/MedImmune Drug Safety.

10.3.2 Reporting of serious adverse events

DSMC SAE Reporting Requirements

The Data Safety Monitoring Committee (DSMC) is responsible for reviewing SAEs for CCCWFU Institutional studies as outlined in Appendix 6. DSMC currently requires that all unexpected 4 and all grade 5 SAEs on these trials be reported to them for review. All CCCWFU Clinical Research Management (CRM) staff members assisting a Principal Investigator in investigating, documenting and reporting an SAE qualifying for DSMC reporting are responsible for informing a clinical member of the DSMC as well as the entire committee via the email notification procedure of the occurrence of an SAE.

WFUHS IRB AE Reporting Requirements

Any unanticipated problems involving risks to subjects or others and adverse events shall be promptly reported to the IRB, according to institutional policy. Reporting to the IRB is required regardless of the funding source,

study sponsor, or whether the event involves an investigational or marketed drug, biologic or device. Reportable events are not limited to physical injury, but include psychological, economic and social harm. Reportable events may arise as a result of drugs, biological agents, devices, procedures or other interventions, or as a result of questionnaires, surveys, observations or other interactions with research subjects.

All members of the research team are responsible for the appropriate reporting to the IRB and other applicable parties of unanticipated problems involving risk to subjects or others. The Principal Investigator, however, is ultimately responsible for ensuring the prompt reporting of unanticipated problems involving risk to subjects or others to the IRB. The Principal Investigator is also responsible for ensuring that all reported unanticipated risks to subjects and others which they receive are reviewed to determine whether the report represents a change in the risks and/or benefits to study participants, and whether any changes in the informed consent, protocol or other study-related documents are required.

Any unanticipated problems involving risks to subjects or others occurring at a site where the study has been approved by the WFUHS IRB (internal events) must be reported to the WFUHS IRB within 7 calendar days of the investigator or other members of the study team becoming aware of the event.

Any unanticipated problems involving risks to subjects or others occurring at another site conducting the same study that has been approved by the WFUHS IRB (external events) must be reported to the WFUHS IRB within 7 calendar days of the investigator or other members of the study team becoming aware of the event.

Any event, incident, experience, or outcome that alters the risk versus potential benefit of the research and as a result warrants a substantive change in the research protocol or informed consent process/document in order to insure the safety, rights or welfare of research subjects.

Sponsor Reporting Requirements

All SAEs will be reported, whether or not considered causally related to the investigational product, or to the study procedure(s). The reporting period for SAEs is the period immediately following the time that written informed consent is obtained through 90 days after the last dose of durvalumab or until the initiation of alternative anticancer therapy. The investigator and/or Sponsor are responsible for informing the Ethics Committee and/or the Regulatory Authority of the SAE as per local requirements.

The investigator and/or sponsor must inform the FDA, via a MedWatch/AdEERs form, of any serious or unexpected adverse events that occur in accordance with the reporting obligations of 21 CFR 312.32, and will concurrently forward all such reports to AstraZeneca. A copy of the MedWatch/AdEERs report must be faxed to AstraZeneca at the time the event is reported to the FDA. It is the responsibility of the sponsor to compile all necessary information and ensure that the FDA receives a report according to the FDA reporting requirement timelines and to ensure that these reports are also submitted to AstraZeneca at the same time.

* A *cover page* should accompany the *MedWatch/AdEERs* form indicating the following:

"Notification from an Investigator Sponsored Study"

The investigator IND number assigned by the FDA

The investigator's name and address

The trial name/title and AstraZeneca ISS reference number (ESR-15-11576).

* Sponsor must also indicate, either in the SAE report or the cover page, the *causality* of events *in relation to all study medications* and if the SAE is *related to disease progression*, as determined by the principal investigator.

* Send SAE report and accompanying cover page by way of email to AstraZeneca's designated mailbox: [contact]

If a non-serious AE becomes serious, this and other relevant follow-up information must also be provided to AstraZeneca and the FDA.

Serious adverse events that do not require expedited reporting to the FDA still need to be reported to AstraZeneca preferably using the MedDRA coding language for serious adverse events. This information should be reported on a monthly basis and under no circumstance less frequently than quarterly.

10.3.3 Reporting of deaths

All deaths that occur during the study, or within the protocol-defined 90-day post-last dose of durvalumab safety follow-up period must be reported as follows:

Death that is clearly the result of disease progression should be documented but should not be reported as an SAE.

Where death is not due (or not clearly due) to progression of the disease under study, the AE causing the death must be reported to as a SAE within **24 hours** (see Section 10.3.2 for further details). The report should contain a comment regarding the co-involvement of progression of disease, if appropriate, and should assign main and contributory causes of death.

Deaths with an unknown cause should always be reported as a SAE.

Deaths that occur following the protocol-defined 90-day post-last-dose of durvalumab safety follow-up period will be documented, but will not be reported as an SAE.

10.3.4 Other events requiring reporting

10.3.5 Overdose

An overdose is defined as a subject receiving a dose of durvalumab in excess of that specified in the Investigator's Brochure, unless otherwise specified in this protocol.

Any overdose of a study subject with durvalumab, with or without associated AEs/SAEs, is required to be reported within 24 hours of knowledge of the event to the sponsor and AstraZeneca/MedImmune Patient Safety or designee using the designated Safety e-mailbox (see Section 10.3.2 for contact information). If the overdose results in an AE, the AE must also be recorded as an AE (see Section 10.3). Overdose does not automatically make an AE serious, but if the consequences of the overdose are serious, for example death or hospitalization, the event is serious and must be recorded and reported as an SAE (see Section 10.1.2 and Section 10.3.2). There is currently no specific treatment in the event of an overdose of durvalumab.

The investigator will use clinical judgment to treat any overdose.

10.3.6 Hepatic function abnormality

Hepatic function abnormality (as defined in Section 10.1.3.3) in a study subject, with or without associated clinical manifestations, is required to be reported as "hepatic function abnormal" *within 24 hours of knowledge of the event* to the sponsor and AstraZeneca Patient Safety using the designated Safety e-mailbox (see Section 10.3.2 for contact information), unless a definitive underlying diagnosis for the abnormality (e.g., cholelithiasis or bile duct obstruction) that is unrelated to investigational product has been confirmed.

- If the definitive underlying diagnosis for the abnormality has been established and is unrelated to investigational product, the decision to continue dosing of the study subject will be based on the clinical judgment of the investigator.
- If no definitive underlying diagnosis for the abnormality is established, dosing of the study subject must be interrupted immediately. Follow-up investigations and inquiries must be initiated by the investigational site without delay.

Each reported event of hepatic function abnormality will be followed by the investigator and evaluated by the sponsor and AstraZeneca/MedImmune.

10.3.7 Pregnancy

10.3.8 Maternal exposure

If a patient becomes pregnant during the course of the study, the IPs should be discontinued immediately.

Pregnancy itself is not regarded as an AE unless there is a suspicion that the IP under study may have interfered with the effectiveness of a contraceptive medication. Congenital abnormalities or birth defects and spontaneous miscarriages should be reported and handled as SAEs. Elective abortions without complications should not be handled as AEs. The outcome of all pregnancies (spontaneous miscarriage, elective termination, ectopic pregnancy, normal birth, or congenital abnormality) should be followed up and documented even if the patient was discontinued from the study.

If any pregnancy occurs in the course of the study, then the Investigator or other site personnel should inform the appropriate AstraZeneca representatives within 1 day, ie, immediately, but **no later than 24 hours** of when he or she becomes aware of it.

The designated AstraZeneca representative will work with the Investigator to ensure that all relevant information is provided to the AstraZeneca Patient Safety data entry site within 1 to 5 calendar days for SAEs and within 30 days for all other pregnancies.

The same timelines apply when outcome information is available.

10.3.9 Paternal exposure

Male patients should refrain from fathering a child or donating sperm during the study and for 90 days after the last dose of durvalumab monotherapy.

Pregnancy of the patient's partner is not considered to be an AE. However, the outcome of all pregnancies (spontaneous miscarriage, elective termination, ectopic pregnancy, normal birth, or congenital abnormality) occurring from the date of the first dose until 90 days after the last dose should, if possible, be followed up and documented.

Where a report of pregnancy is received, prior to obtaining information about the pregnancy, the Investigator must obtain the consent of the patient's partner. Therefore, the local study team should adopt the generic ICF template in line with local procedures and submit it to the relevant Ethics Committees (ECs)/Institutional Review Boards (IRBs) prior to use.

11. STATISTICAL METHODS AND SAMPLE SIZE DETERMINATION

11.1 Description of analysis sets

Primary Objectives

The primary objectives of this pilot study are to investigate the effect of Durvalumab on local and systemic immune activation and compare the results in HPV positive and HPV negative patients with oral cavity and oropharynx HNSCC. Tumor tissue, blood and saliva will be collected before and after treatment with Durvalumab and will be analyzed for systemic immune response to HPV and tumor associated antigens and impact on immune regulatory mechanisms in tumor and blood. Levels of immune-regulatory miR in plasma and saliva will be correlated with other parameters of the local and systemic immune response in order to identify possible predictors of response. Results will be compared between HPV positive and negative patients to identify a possible differential effect of treatment with Durvalumab. Level of local immune response in the primary tumor and in the regional lymph nodes will be compared whenever possible.
Secondary Objectives

- A. Investigate the effect of the treatment with Durvalumab on measures of tumor volume (from the CT scan) and tumor activity (from the PET scan).
- B. Evaluate the safety of a short induction treatment with Durvalumab.

Primary Endpoints:

Since this is a pilot study and does not have a specific primary efficacy analysis, there are several primary endpoints (rather than a single primary efficacy endpoint) that will be collected. These can be described in three broad categories within the area of local and systemic immune activation. The categories are effects of Durvalumab on 1) systemic immune response to HPV and tumor associated antigens; 2) immune regulatory mechanisms; and 3) immune-regulatory miR responses as measured in plasma, saliva or tumor. Each of these categories has several endpoints that will now be described.

- 1. Systemic immune response to HPV and tumor associated antigens:
 - a. Peripheral blood mononuclear cell interferon-γ production in vitro (ELISA) in response to commercially available peptide pools corresponding to HPV, p53, Mage-A3, Her2/neu, and survivin will be determined.
- 2. Immune regulatory mechanisms.
 - a. The following immune effector and regulatory responses will be assessed in blood using standard flow cytometric techniques: CD4+, CD8+, CD4+FoxP3+ Treg, and CD45RO+CD4+ memory T cells; CD3-CD56+ NK cells, and CD14-HLA-DR-CD15+ MDSC.
 - b. Tumor (primary tumor and regional involved lymph nodes) will be collected before treatment and at the time of surgery, after treatment. PD-1+CD4+, PD 1+CD8+, PD-1L+, and Foxp3+CD4+ tumor-infiltrating cells will be quantified (0 to 3+) using standing immunofluorescence techniques.
- 3. Immune-regulatory miR response.
 - a. Levels of immune-regulatory miRs in blood, saliva and tumor (primary and regional involved lymph nodes) will be quantified using PCR-based techniques.

Secondary Endpoints

There are two types of secondary endpoints.

The first consist of measures of tumor volume (via CT scan) or metabolic activity (via PET scan).

The second are measures of clinical toxicities that may occur during the trial.

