^a Should be obtained from the initial diagnostic biopsy. In exceptional cases when not enough tissue is available, it can be performed on tissue obtained with research biopsy or on the surgical specimen. This option is not available when one of the study arms completed accrual. HPV status must be known before at time of screening.

^b Pre-menopausal female subjects of childbearing potential only

Clinical Study Protocol Drug Substance Durvalumab (MEDI4736) Study Number **ESR-15-11576** Edition Number 5 Date 05/23/16 WFU Date 05/18/21

^c Full physical examination at baseline; targeted physical examination at other timepoints

^d Subjects will have their blood pressure and pulse measured before, during and after the infusion at the following times (based on a 60-minute infusion):

- At the beginning of the infusion (at 0 minutes)
- At 30 minutes during the infusion (±5 minutes)
- At the end of the infusion (at 60 minutes ± 5 minutes)
- In the 1 hour observation period post-infusion: 30 and 60 minutes after the infusion (ie, 90 and 120 minutes from the start of the infusion) (±5 minutes) for the first infusion only and then for subsequent infusions as clinically indicated
- If the infusion takes longer than 60 minutes then blood pressure and pulse measurements should be collected every 30 minutes (±5 minutes) and as described above or more frequently if clinically indicated.

^e ECG during screening and at Day1 –baseline. Thereafter as clinically indicated. Baseline and abnormal ECG at any time in triplicate others single. 1 ECG is needed while on treatment, and as clinically indicated. ECGs should be taken within an hour prior to the start of the infusion and at least one time point 0 to 3 hours after the infusion.

^f If screening laboratory assessments are performed within 3 days prior to Day 1 they do not need to be repeated at Day 1. Results for safety bloods must be available and reviewed before commencing an infusion. Creatinine clearance, gamma glutamyltransferase, magnesium, and uric acid testing are to be performed at screening, on Day 1 (unless screening laboratory assessments are performed within 3 days prior to Day 1), and if clinically indicated.

^g Free T3 and free T4 will only be measured if TSH is abnormal. They should also be measured if there is clinical suspicion of an adverse event related to the endocrine system. ^h Urinalysis performed at Screening, Day 1, and as clinically indicated.

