1.3 Research hypothesis

Based on preliminary data showing that the presence of HPV antigens is contributing to increased anti-tumor T cell activity in patients with SCCHN, we hypothesize that immunotherapy with PD-L1 antibody will lead to more intense and efficient specific immune activation against the SCCHN tumor in HPV + patients compared with HPV - patients. We also hypothesize that an extensive analysis of the blood and saliva might lead to identification of markers predictive of a more efficient response to PD-L1 inhibition. Lastly we would like to test the ability of PET scan to detect an increased immune response. One can hypothesize that a corresponding increase in the immune response with an increase in the number of infiltrative activated immune cells could be associated with an increase in metabolic activity measured by PET SUV. Similarly, an effective anti-tumor activity of the

activated immune response could lead to decreased metabolic activity. We are interested in evaluating the dynamic in the metabolic activity early in the treatment and to attempt to detect potential consistency that could be used in future therapeutic paradigms.

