3. STUDY DESIGN

3.1 Overview of study design

This is a non-randomized, open label, uncontrolled, single group assignment study, to evaluate the anti-tumor effect of Durvalumab in patients with HNSCC when given as a short treatment course before surgery.

A schematic diagram of the overall study design is shown below.

Patients must be scheduled for surgery and have a window of at least 3 weeks between the time of diagnosis and time of surgery.

In order to be eligible for this clinical study, the patients must have fresh tumor tissue frozen and saved in our Tumor Tissue Bank or need to consent for an additional biopsy procedure to obtain a tumor tissue sample for the clinical protocol that will be saved in our Tumor Tissue Bank for the correlative studies. Patients will undergo an assessment on their tumor tissue sample to determine HPV status.

10 HPV+ and 10 HPV- patients will be initially enrolled and need to complete the study. If any patient does not complete the study treatment and investigations, the patient will be replaced.

First administration of Durvalumab will be given with the first visit after registration with the clinical study. Second administration of Durvalumab will be given 2 weeks later. An interval of 3 to 17 days must be ensured for all patients between the last administration of drug and surgery. A 7-14 days interval will be strongly considered and attempted in each case. In the rare circumstances in which surgery was scheduled or delayed at more than 2 weeks after second administration of Durvalumab, a third administration of drug must be given in order to ensure the proposed interval between the last dose of Durvalumab and surgery.

After surgery the patients may proceed with adjuvant treatment as indicated by the stage of their disease and by the surgical pathology findings. A Radiation Oncologist is included in the study team in order to address and to include in the therapeutic algorithm the impact of the potential cytoreduction by Durvalumab therapy on the final surgical and pathologic staging.

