Tumor (primary tumor and involved lymph node) will be assayed using standing immunofluorescence techniques for PD-1+CD4+, PD 1+CD8+, PD-1L+, and Foxp3+CD4+ tumor-infiltrating cells. The results will be quantified (0 to 3+).

Immunohistochemical staining will be carried out on 4µm-thick sections utilizing an Autostainer Plus (Dako - Agilent Technologies) with appropriate positive and negative controls. Sections are baked for 60 minutes at 60 °C in a dehydration oven and heat-induced epitope retrieved in the PT link (Dako – Agilent technologies) using EnVision FLEX target retrieval solution for 20 minutes at 97 °C then cooled to room temperature in TBST Wash buffer for 5 minutes. Slides are incubated with the diluted antibodies. Antibody detection will utilize the Envision FLEX kit (K8023) with a DAB chromagen for visualization according to the manufacturer's instructions (Dako – Agilent technologies). Slides are then counterstained with hematoxylin. The percentage of tumor which have an infiltrate of lymphocytes or macrophages will be estimated and the average number of positive immune cells per high power field (HPF) in a minimum of 4 representative HPF areas will be determined utilizing a semi-quantitative four tiered scale used for scoring lymphocytes (0= no lymphocytes, 1= 1-10/HPF, 2= 11-50/HPF and 3= >50/HPF) and macrophages (0= no macrophages, 1= 1-50/HPF, 2= 50-100/HPF and 3=>100/HPF). Lymphocyte and macrophage infiltrate scores are obtained by multiplying these scores to attain a score from 0-300.

miRNA will be quantified in tumor tissue and involved lymph node using PCR-based techniques (as described in 8.3.1).

Remaining tissue samples will be retained for future research after the study report has been finalized if agreed by patients in the ICF. Otherwise it will be disposed.

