9.1.1. CT Scan or MRI

CT scan or MRI will be obtained before (within 14 days) treatment with Durvalumab and before surgery. Results of the CT scan or MRI performed after treatment with durvalumab will be compared and reported to the results of the same imaging study performed initially, before treatment. Both imaging evaluations (before and after treatment) should be performed using the same techniques and results will be interpreted by the same radiologist.

In interpretation of the results, the following will be considered:

The response to immunotherapy may differ from the typical responses observed with cytotoxic chemotherapy including the following (Wolchok et al 2009, Nishino et al 2013):

- Response to immunotherapy may be delayed
- Response to immunotherapy may occur after PD by conventional criteria
- The appearance of new lesions may not represent PD with immunotherapy
- SD while on immunotherapy may be durable and represent clinical benefit.

RECIST 1.1 criteria will be used to measure tumor size. However, based on the above considerations, the standard RECIST criteria will not be used to measure response. We will report percentage change in tumor measurements before and after treatment in each patient.

Only patients with measurable disease at baseline should be included in the study. Measurable disease is defined by the presence of at least 1 measurable (by RECIST 1.1) lesion.

Measurable: A lesion, not previously irradiated per the protocol prior to enrollment, that can be accurately measured at baseline as ≥ 10 mm in the longest diameter (except lymph nodes which must have short axis ≥ 15 mm) with CT or MRI and that is suitable for accurate repeated measurements.

Non-measurable:

- All other lesions, including small lesions (longest diameter <10 mm or pathological lymph nodes with ≥ 10 mm to <15 mm short axis at baseline).
- Truly non-measurable lesions include the following: bone lesions, leptomeningeal disease, ascites, pleural/pericardial effusion, inflammatory breast disease, lymphangitic involvement of skin or lung, or abdominal masses/abdominal organomegaly identified by physical examination that is not measurable by CT or MRI.
- Lesions <2 cm biopsied within the screening period (newly acquired tumor biopsy).

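### The 0 to 3+ tumor-infiltrate score (primary endpoint 2b) appears to rest on reader judgement, and nothing masks the reader to HPV status, so expectation can bias the HPV comparison

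*Combined protocol and SAP*

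**What the plan says.** **Endpoint.** Item 2b of the primary endpoints in Section 11.1 covers PD-1+CD4+, PD-1+CD8+, PD-L1+ and Foxp3+CD4+ cells in tumor and involved nodes, before and after treatment: "tumor-infiltrating cells will be quantified (0 to 3+) using standing immunofluorescence techniques".

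**Scoring.** Section 8.3.4 names the same immunofluorescence grade and then describes a chromogenic immunohistochemistry procedure. There, "The percentage of tumor which have an infiltrate of lymphocytes or macrophages will be estimated". Separately, positive cells are averaged over at least four representative high-power fields and graded on a "semi-quantitative four tiered scale used for scoring lymphocytes" (0, 1–10, 11–50, more than 50 per field), with a parallel scale for macrophages. No reader, second reader, image-analysis software or masking is named.

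**Analysis.** Section 11.2.2, item 3, compares HPV groups on the tissue score by Fisher exact tests before and after treatment, and uses Stuart-Maxwell tests for change.

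**Knowledge of HPV status.** Section 3.1: "This is a non-randomized, open label, uncontrolled, single group assignment study". Footnote a to the schedule of assessments: "HPV status must be known before at time of screening". The same footnote lets HPV testing use the research biopsy or surgical specimen in exceptional cases. Section 8.1.1 lets the result be pending at enrolment while neither group is full.

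**Expected direction.** Section 1.3 states that PD-L1 immunotherapy "will lead to more intense and efficient specific immune activation against the SCCHN tumor in HPV + patients compared with HPV - patients".

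**Masking.** The only blinded step is in Section 9.1.1: a physician's review of flagged CT or MRI lesions too large to measure. It does not say what is masked, and it does not concern tissue.

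**The concern.** The HPV contrast is the trial's central question, and Section 1.4 intends the results to inform the differential role of immunotherapy by HPV status. Where a score depends on estimating an extent and choosing representative fields, a reader who knows a patient's HPV status and the predicted direction can lean towards that prediction without intending to.

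Such a lean is systematic. It shifts the estimated difference itself, and averaging over patients does not remove it. The plan has no second reading from which the shift could be measured. Because a pilot is read mainly through its estimates, the harm does not depend on a test reaching significance.

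**Working it through.** **1. The plan's own figures.** Section 11.3 gives 10 patients per group, a 95% confidence half-width of 0.72 SD, and 80% power for 1.3 SD.
- Half-width: t(0.975; 9)/√10 = 0.715, which rounds to 0.72.
- Power: a two-sided two-sample t-test with 18 degrees of freedom has 78.5% at 1.3 SD (82.8% by the normal approximation).

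Both agree closely with the plan. The point does not rest on an arithmetic error, and masking leaves the sample size unchanged. These figures concern t-tests; the tissue score is tested by Fisher's exact test.

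**2. Is the reader exposed?**
- Judgement enters the score: the percentage is estimated and the fields are representative ones (8.3.4).
- HPV status is available: normally at screening; if pending then, nothing keeps the later result from the reader.
- A direction is stated (1.3).
- No masking of the tissue reader appears anywhere.

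**3. Possible size, under assumptions.** Inputs from the documents: 10 versus 10, four tiers, Fisher's exact test. Assumed: alpha 0.05 for this test, as Section 11.3 gives for the t-test; no true HPV difference; HPV-negative scores read correctly; each HPV-positive score below 3 raised one tier with probability q; and two sets of true tier frequencies.

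With true frequencies p0, p1, p2, p3, the HPV-positive group is read as:
- tier 0: p0(1 − q)
- tier 1: p1(1 − q) + p0·q
- tier 2: p2(1 − q) + p1·q
- tier 3: p3 + p2·q

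The mean rises by q × (p0 + p1 + p2). For 20/30/30/20% this is 0.8q; for 10/40/40/10% it is 0.9q. For example, at q = 0.4 the first set is read as 12/26/30/32%.

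The rejection rate is the sum, over all pairs of possible 10-patient score tables, of the probability of each pair whose exact 2×4 Fisher p-value is at most 0.05.

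| q | Shift, 20/30/30/20% | False positives | Shift, 10/40/40/10% | False positives |
|---|---|---|---|---|
| 0 | 0 | about 4% | 0 | about 4% |
| 20% | 0.16 tiers | about 5% | 0.18 tiers | about 5% |
| 40% | 0.32 tiers | about 7% | 0.36 tiers | about 9% |
| 60% | 0.48 tiers | about 10% | 0.54 tiers | about 17% |

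The rates are for one cell population at one time point. Four populations are scored, so the error can recur. Both frequency sets are symmetric, so a downward lean of the same kind gives the same rates.

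**The case against.** **How the score is read is partly inferred.** The detailed scoring text in Section 8.3.4 is for immunohistochemistry of lymphocytes and macrophages, while endpoint 2b is an immunofluorescence grade whose reading is not separately described. The numeric cut-points also limit free judgement and make the higher upgrade rates less plausible. This stands, and it is why the point says that the score appears to rest on judgement. The cut-points do not govern which fields are chosen or how the percentage is estimated.

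**Direction.** The hypothesis is about immune activation overall and gives no direction for each population. For Foxp3+CD4+ regulatory cells a reader might expect less rather than more. That changes the sign of a possible lean, not the exposure.

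**Scope.** The study is a descriptive pilot. ELISA, flow cytometry and PCR endpoints are instrument-based and much less exposed. Tissue-bank database access is limited to core staff, and nothing shows that the scorer consults HPV results. This limits the reach of the point, but restricted access to a database is not masking.

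**The change score.** If HPV status influences both visits equally, bias in the change partly cancels. The separate pre- and post-treatment Fisher tests remain exposed.

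**CT and MRI.** A reader might extend the point to imaging because "results will be interpreted by the same radiologist" and no masking is stated. The documents do not support that extension. Imaging size is secondary, follows RECIST 1.1 measurement rules and has no HPV-directed hypothesis. Using one radiologist is a consistency control. Section 4.1 puts oral cavity cancers at more than 90% HPV negative and oropharynx cancers at about 60–80% HPV positive, so the tumor site on the scan largely reveals HPV status anyway.

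**Conclusion.** The point holds for primary endpoint 2b and should be acted on. The plan compares HPV groups on a score that appears to depend on reader judgement, states which group should respond more strongly, and does not mask the reader.

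The size is unknown. Under the assumed upgrade rates of 20% to 60%, false positives per population and time point rise from about 4% to between 5% and 10%, or between 5% and 17%, depending on the tier frequencies. At the lowest rate the test is barely affected, although the estimated mean difference still moves by 0.16 to 0.18 tiers.

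Three stronger inferences are not supported:
- That open-label treatment is the source. Every patient receives durvalumab; the source is knowledge of HPV status and, for change, of the visit.
- That bias is shown to occur. The documents show an unprotected comparison, not a biased reading.
- That unmasked scores could never be repaired. A coded re-read is possible while slides or tissue remain, although Section 8.3.4 keeps leftover tissue beyond the final report only with the patient's agreement.

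**What to change.** Add to Section 8.3.4:
- The Tumor Tissue Bank relabels pre- and post-treatment slides with a study code that reveals neither patient, HPV status nor visit.
- The same pathologist scores all slides as a batch, in random order, without HPV status or visit label.
- HPV status and visit are linked to the scores only after the scores are locked.

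The cost is relabelling work and waiting to read in a batch. No extra reader, procedure, visit or patient is needed. Masking will be partial: a biopsy may be told from a resection, and tumor site, which is related to HPV status, may sometimes be recognisable on the slide. The report should say so. No change to Section 9.1.1 is asked for.
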